9.0 CLINICAL AND LABORATORY EVALUATIONS AND STUDY CALENDAR

Parameter	Pre-	Day 1	Weekly	Bi-monthly
	Treatment			
Targeted History (alcohol history, psychiatric history, liver transplant history, medications history, social history, abdominal imaging, pregnancy test if indicated)	X			
Complete Blood Count (CBC)	X			X
Complete Metabolic panel (CMP)	X			Χ
Alcohol Metabolites	Х	-		X

Immunosuppression levels	X			Х
Penn Alcohol Craving Scale (PACS)	X		X	
Quick Drinking Screen	X		X	
Timeline Follow back	X		X	
General Assessment of Side Effects in			Х	
Clinical Trials (GASE)				
Agent administration		X^1		
Interval history (hospitalizations,			X	
medication changes)				

¹daily

10.0 CRITERIA FOR EVALUATION AND ENDPOINT DEFINITIONS

Outcomes assessed will include feasibility, safety, and efficacy. Feasibility will be assessed via completion rates, number of missed doses per patient, and number of patients who completed 3 monthly refills for the study. Safety will be measured via % total, minor, moderate, and major side-effects documented via the GASE survey and mortality during the time of the study. Finally, efficacy will be measured via % maintained abstinence, reduction in alcohol cravings determined via PACS score, and % of alcohol relapses determined via TLFB survey, PeTh, and self-reporting. We will then examine acamprosate use and its effect on 1-, 3-, and 5- year graft survival and alcohol usel in our patients transplanted for ALD. Efficacy and safety outcomes will be compared to control group to determine if acamprosate itself is helpful and safe for alcohol use reduction post-LT.

11.0 SPECIAL INSTRUCTIONS:

This is not applicable for this study.

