- 1.2 Acamprosate is an effective FDA approved adjunct therapy for alcohol dependence in adults⁸. However, there is limited literature on the use of acamprosate in patients with ALD, and there is no literature on the use of acamprosate in post-LT ALD patients^{7,8}. It is well established that acamprosate is not metabolized by the liver and unlikely to interfere with medications metabolized via cytochrome P450⁸. Given this unique pharmacokinetic property of acamprosate, there should be no drug-drug interactions with its use in LT recipients⁹.
- 1.3 We hypothesize that acamprosate will be a feasible AUD therapy for post-LT patients.

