2.0 OBJECTIVES AND PURPOSE

Keck Medicine of USC's Liver Transplant Program will develop a pilot study to incorporate acamprosate use in suitable post-LT individuals. A research team will provide weekly appointments to administer surveys to assess for alcohol use, alcohol cravings, acamprosate compliance, and drug side-effects. Patients will obtain laboratory values and visit their transplant hepatologist monthly as is standard of care. Patients will also receive a consultation with the program's transplant pharmacist to reconcile medications to avoid drug-drug interactions.

The primary goals of this study are:

- 2.1 To evaluate the feasibility and safety of acamprosate for management of AUD in post-liver transplant patients
- 2.2 To determine whether acamprosate use in combination with standard of care (weekly telephone visit) reduces the frequency of alcohol relapse

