12.0 DATA COLLECTION AND MONITORING

All data collection will be done using the REDCAP database. Only those involved in data collection and analysis who are included on the IRB will have access to the data.

13.0 STATISTICAL CONSIDERATIONS

13.1 The goal of this study is to evaluate the feasibility, safety, and efficacy of acamprosate for management of AUD in post-liver transplant patients. All patients will be post-LT with a pre-LT diagnosis of ALD. As our usual number of transplants per year is 120 and 30% of patients have ALD (includes AH) as a diagnosis, we do not anticipate any difficulties in identifying 30 participants for this study. Feasibility will be assessed via completion rates, number of missed doses per patient, and number of patients who completed 3 monthly refills for the study. Safety will be measured via % total, minor, moderate, and major side-effects documented via the GASE survey. Finally, efficacy will be measured via % maintained abstinence, reduction in alcohol cravings determined via PACS score, % of alcohol relapses determined via TLFB survey, PEth, and self-reporting and patient and graft survival in our patients transplanted for ALD. Demographic variables will be compared between SOC and acamprosate+SOC groups using descriptive statistics. Efficacy and safety outcomes will be compared to control group using wilcoxan pair rank sum. Cox regression analysis will be done to determine determinants of alcohol relapse and graft failure in both SOC and SOC+acamprosate

group. Finally, time to relapse will be measured in both SOC and SOC+acamprosate group via Kaplan meier plots.

13.2 Given the small number of patients (30), we will not perform a stratified randomization based upon age, race, ethnicity and timing from transplant but rather compare frequencies of different ethnicities in our descriptive statistics section.

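### A 25–30 patient pilot promises to determine whether acamprosate works, from several efficacy outcomes with none designated as the lead

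*Combined protocol and SAP*

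**What the plan says.** Section 2.0 states that the programme "will develop a pilot study to incorporate acamprosate use in suitable post-LT individuals". Section 1.3 gives one hypothesis: "We hypothesize that acamprosate will be a feasible AUD therapy for post-LT patients". Under the words "The primary goals of this study are", section 2.0 then lists two goals: feasibility and safety (2.1), and an efficacy goal (2.2): "To determine whether acamprosate use in combination with standard of care (weekly telephone visit) reduces the frequency of alcohol relapse".

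Section 10.0 gives the on-study efficacy outcomes: "efficacy will be measured via % maintained abstinence, reduction in alcohol cravings determined via PACS score, and % of alcohol relapses", with relapse taken from TLFB, PEth and self-report. It adds an examination of acamprosate use and "its effect on 1-, 3-, and 5- year graft survival and alcohol usel in our patients transplanted for ALD". It closes by saying that efficacy and safety outcomes will be "compared to control group to determine if acamprosate itself is helpful and safe for alcohol use reduction post-LT".

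Section 13.1 repeats the on-study list and puts patient and graft survival under efficacy. It then gives one comparison method: "Efficacy and safety outcomes will be compared to control group using wilcoxan pair rank sum". It also mentions Cox regression for determinants of relapse and graft failure, and Kaplan-Meier plots of time to relapse.

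The target of 25–30 patients (section 5.0) is supported by recruitment capacity only. No significance level, primary efficacy endpoint, testing order or multiplicity rule is given.

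**The concern.** The stated purpose and the design do not match. A feasibility pilot can estimate an effect with a wide interval. It cannot settle whether a drug reduces relapse, yet two sections say that it will.

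The mismatch matters because the efficacy list is open-ended. Relapse is the outcome in goal 2.2, but the endpoint and analysis sections give it no priority over craving, later alcohol use or survival, and do not say when it is read or how its three sources combine. If all the outcomes go through a rank-sum test, a chance difference in one of them could be reported as showing that acamprosate is helpful, and the plan contains nothing to stop that. A later trial, or off-protocol prescribing to transplant recipients, could then rest on a chance finding.

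**Working it through.** **Plan's own figure.** There is none to reproduce: the plan states no error rate or power.

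**Inputs from the documents.** 25–30 patients at 2:1, so about 20 v 10 at N = 30 (section 5.0); outcome lists (sections 10.0 and 13.1); the test, read as the rank-sum test for independent groups (section 13.1).

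**Inputs assumed.** Two-sided 5% per test; correlation between outcomes 0 to 0.6; event rates, for example relapse 20%, alcohol use 20/35/50% and graft loss 8/15/20% at 1, 3 and 5 years, and death 10%.

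**Count.**
- Alcohol outcomes: relapse (abstinence is its complement) 1 + PACS 1 + alcohol use at 1, 3 and 5 years 3 = 5.
- Adding graft survival at 1, 3 and 5 years (3) and patient survival (1): 5 + 4 = 9.

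**Upper reference, independent tests of exact 5% size.**
- Five: 1 − 0.95^5 = 22.6%.
- Nine: 1 − 0.95^9 = 37.0%.

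**Effect of correlation between the test statistics** (simulated, all pairs equally correlated, each test of exact 5% size):

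| Correlation | Five tests | Nine tests |
|---|---|---|
| 0.3 | 20.8% | 32.6% |
| 0.6 | 16.6% | 23.7% |
| 0.9 | 10.1% | 12.3% |

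**Small-sample simulation, 20 v 10, no drug effect, rank-sum tests.** With few events a binary outcome often cannot reach p<0.05, so the totals fall below the independence figures even at zero correlation. Range across runs with different assumed rates and correlations of 0 to 0.6:

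| Outcomes | At least one p<0.05, either direction | At least one p<0.05 favouring acamprosate |
|---|---|---|
| Five alcohol outcomes | 17–20% | 10–13% |
| All nine | 25–32% | 18–24% |

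**Why more than half the chance findings favour the drug.** With 2:1 allocation the rank-sum test is lopsided for rare events. Take 0/20 v 2/10. U lies 20 from its mean of 100. Its tie-corrected variance is (200/12) × [31 − (28³ − 28 + 2³ − 2)/(30 × 29)] = 96.55, SD 9.83. Then z = (20 − 0.5)/9.83 = 1.98, p = 0.047. In the other direction, 6/20 v 0/10 is not enough: U lies 30 from its mean, SD 15.76, z = 29.5/15.76 = 1.87, p = 0.06. It takes 7/20 v 0/10. Two control events with none on acamprosate suffice to favour the drug; seven acamprosate events with none on control are needed to go against it.

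**Dependence on the test.** Runs with Fisher tests for the binary outcomes, on slightly different sets of nine, gave about 11–19% in either direction.

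**With one pre-named lead outcome** the chance is at most about 5% by construction.

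**The case against.** The strongest reply is that the family of tests is the reader's construction. Section 10.0 says only that the long-term outcomes will be examined. Section 13.1 lists patient and graft survival without splitting them by year, and assigns Cox regression to relapse and graft failure. Neither section says that each time point gets its own test or that one positive result counts as success. Section 10.0 puts on-study mortality under safety, so patient survival is an efficacy outcome only on section 13.1's list. Section 10.0 also ties helpfulness to alcohol use reduction, which a survival difference would not show. All of this stands. It is why the five-outcome figures come first and the nine-outcome figures are conditional. It does not remove the problem: section 13.1 sends efficacy outcomes as a group to one test, and no rule excludes a claim from any of them.

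A second reply is that goal 2.2 does name an outcome. That is right. What is missing is its designation as the lead outcome in sections 10.0 and 13.1, with a time point and a definition.

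Two stronger readings are tempting and should not be made:

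- *That the plan carries a false-positive chance of a quarter to a third.* This needs all nine outcomes to be tested separately, counts results against acamprosate as well as for it, and rests on a significance level, event rates and correlations that the documents do not give.
- *That relapse has almost no chance of showing an effect, so any claim must come from elsewhere.* The roughly 50% relapse by 5 years in section 1.1, at constant hazard, gives 1 − 0.5^(98/1826) = 3.65% in 14 weeks, or 0.37 expected relapses among 10 controls. If acamprosate prevented every relapse, the chance of the two or more control relapses needed would be 4.9%. But the plan sets no limit on time from transplant and requires no abstinence at entry, so the 14-week risk is unknown. The same chance is 26% at a 10% risk and 62% at 20%. The two-relapse threshold also holds only for the normal approximation; Fisher's test gives p = 0.103 for 0/20 v 2/10.

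**Conclusion.** The concern holds as a mismatch between the claim and the design. The text itself establishes three things: two sections promise a determination, the only hypothesis is feasibility, and no efficacy outcome is given the lead or any error control. That part needs no assumption.

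The size does. Under the assumptions listed, a false signal favouring acamprosate has a chance of about 10–13% over the five alcohol outcomes, and 18–24% if all nine are tested. A two-sided 5% test of one outcome would allow about 2.5% in that direction (half of 5%), and its lopsidedness at 2:1 makes that approximate. The percentages are illustrations, not properties of the plan. In either direction, every setting tried for the nine outcomes exceeded 5%, including those with Fisher tests. The change is worth making before analysis; it does not call the trial's feasibility aim into question.

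**What to change.** - In goal 2.2 and section 10.0, replace determine with estimate.
- In sections 10.0 and 13.1, name relapse by week 14 (the study period in section 3.0), compared by randomised arm, as the single lead efficacy outcome. State how TLFB, PEth and self-report combine to define it. Report it as a risk difference with an exact 95% interval.
- Label all other efficacy comparisons exploratory, each with an estimate and interval, and state that no claim of benefit will be drawn from a p-value among them.

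The cost is protocol and analysis wording only; no patients, visits or data change. The downside is that the sponsor gives up a headline efficacy claim, which this pilot could not support in any case.

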5.0 SELECTION AND WITHDRAWAL OF SUBJECTS

Beginning January 1st, 2022, we will recruit patients from Liver Transplant Program from the USC Transplant Institute's patient census. We will target at least 25-30 patients for this study with 2:1 randomization (acamprosate plus SOC vs SOC alone). All patients must have history of LT with a pre-LT diagnosis of ALD. As our usual number of transplants per year is 120 and 30% of patients have ALD (includes AH) as a diagnosis, we do not anticipate any difficulties in identifying 30 participants for this study.

Enrollment will be on a rolling basis.

- 5.1 Patients must have received a transplant for liver disease secondary to alcohol-associated hepatitis or alcohol-associated cirrhosis.
- 5.2 We will exclude patients with hypersensitivity to acamprosate calcium or any of its components, severe renal impairment (creatinine clearance ≤30 mL/min), psychopathology under treatment with psychoactive drug, substance dependence other than THC, alcohol, or nicotine, need for inpatient detoxification or inpatient treatment of alcohol use, participation in a clinical trial within the past 30 days, and women of childbearing potential who do not practice a medically acceptable form of contraception will be excluded.

We will obtain an informed consent for all patients. As part of the informed consent, participants will be expected to complete a weekly telemedicine visit with a research member for at least 3 months, required to fill out weekly surveys (Appendix III) (Penn Alcohol Craving Scale (PACS), Alcohol Timeline Followback (TLFB), and Generic Assessment of Side Effects in Clinical Trials (GASE) prior to these visits and expected to be compliant with acamprosate if randomized to that group. The proportion of patients eligible but who did not agree to participate will be captured.

5.3 Patients may withdraw from study at any time. If patients suffer any severe adverse effects from acamprosate they will be advised to stop the drug immediately and withdraw from the study.

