6.0 STRATIFICATION/DESCRIPTIVE FACTORS/RANDOMIZATION SCHEME

- 6.1 Sex will be balanced across treatment arms due to the pilot nature of this study, age, race ethnicity and time from transplant will be recorded for planning of future trials.
- 6.2 Drinking history, social history, pre-liver transplant relapse probability scores, medical history, and medication history will be obtained.
- 6.3 Randomization will occur via an unblinded 2:1 ratio of acamprosate plus SOC versus SOC alone respectively stratified by sex.

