7.0 STUDY AGENT ADMINISTRATION OR INTERVENTION AND TOXICITY MANAGEMENT PLAN

7.1 Treatments

A. Standard of Care (SOC): Participants will be expected to complete a weekly telemedicine visit with a research member for at least 3 months, required to fill out weekly surveys (figure 2) (Penn Alcohol Craving Scale (PACS), Alcohol Timeline Followback (TLFB), and Generic Assessment of Side Effects in Clinical Trials (GASE) prior to these visits and expected to be compliant with acamprosate if randomized to that group.

B. SOC+ Acamprosate: Participants randomized to this arm will participate in SOC + take acamprosate 666 mg TID daily for three months.

7.21

AGENT	DOSE	ROUTE	DAYS	ReRx INTERVAL	NOTES
Acamprosate	666 mg	PO TID	Daily	4 weeks	maximum cumulative dose 500 mg/m ²

- 7.31 A patient may always be removed from treatment whenever he/she wishes
- 7.32 Treatment will be discontinued or held at discretion of investigators if patients experience any moderate-severe side effects as evaluated in section 8.0 thought to be secondary to acamprosate.

8.0 ASSESSMENT OF EFFICACY AND SAFETY

8.1 Acamprosate's package insert includes a comprehensive list of adverse events in over 7000 patients exposed to acamprosate¹⁴. However, adverse events are listed without regard to the causal relationship of the events to the drug¹⁴. Only diarrhea and flatulence appear to be significantly associated with acamprosate¹⁴. There is no evidence that acamprosate has additional risks in the liver transplant population⁸. Multiple meta analyses have found that the only side effect significantly associated with acamprosate over placebo is diarrhea^{8,15}. Flatulence is the only other adverse effect that has been significantly associated with acamprosate over placebo¹¹. In a review of clinical trials, diarrhea was observed in 10-17% of patients treated with acamprosate (versus 10-11% in placebo)^{11,12}. Diarrhea appears to be acamprosate dose dependent, settles within a few days, and mostly mild or moderate in severity¹¹. If diarrhea was severe, temporary dose reduction was beneficial⁸. Of note, no statistically significant differences were observed between groups (acamprosate versus placebo) in terms of premature withdrawals from treatment due to adverse effects¹². No clinically meaningful differences have been found comparing acamprosate and placebo regarding the incidence of clinically significant postbaseline abnormalities for any hematology

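### Safety is to be determined by a rank-sum comparison of about 20 vs 10 patients, with no interval or criterion; a non-significant result could be misread as evidence of safety

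*Combined protocol and SAP*

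**What the plan says.** Safety is one of the primary goals (Section 2.1). Section 10.0 defines how it is measured: "Safety will be measured via % total, minor, moderate, and major side-effects documented via the GASE survey and mortality" during the study. It then states the purpose of comparing efficacy and safety with the control group: "to determine if acamprosate itself is helpful and safe for alcohol use reduction post-LT". Section 13.1 repeats the side-effect percentages and gives the method in one sentence: "Efficacy and safety outcomes will be compared to control group using wilcoxan pair rank sum". I take this to be the unpaired Wilcoxon rank-sum test, since the arms are independent.

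On size, Section 5.0 says "We will target at least 25-30 patients for this study with 2:1 randomization (acamprosate plus SOC vs SOC alone", and Section 13.2 works with 30. The number is supported only by how many patients are available. No alpha, power, safety margin, unacceptable event rate or confidence interval appears anywhere.

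Section 8.1 gives event rates for one drug-related effect: "diarrhea was observed in 10-17% of patients treated with acamprosate (versus 10-11% in placebo").

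**The concern.** A comparison whose purpose is to determine safety needs a rule that turns its result into a statement about safety. The plan gives a test and no rule. A test against control is built to show a difference. When it is not significant in a small sample, it says little about which differences remain possible.

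If the report leans on that test, the likely result is a finding of no significant difference. That finding would be compatible with no excess of side effects and also with a substantial one. Section 1.2 says there is no literature on acamprosate in post-transplant patients with alcohol-associated liver disease, so whatever this trial says about safety may carry weight. Percentages without intervals would not show a reader how much remains open.

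**Working it through.** The plan has no power figure to reproduce, so the check asks what the named test can detect.

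**Inputs**
- Arms: 30 patients at 2:1 gives n1 = 20 on acamprosate and n2 = 10 on control (Sections 5.0, 6.3, 13.2). At 25 patients it is about 17 vs 8.
- Rates: 10-17% on acamprosate and 10-11% on placebo (Section 8.1). The widest contrast is 17% vs 10%.
- Assumed: two-sided alpha 0.05, no dropout, and one yes/no outcome per patient.

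**Test statistic.** For a yes/no outcome with N = n1 + n2 and pooled proportion p, the tie-corrected rank-sum statistic is

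z = (p1 − p2) / √[ p(1 − p) · (1/n1 + 1/n2) · N/(N − 1) ].

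Power is the sum of Bin(a; 20, p1) × Bin(b; 10, p2) over all tables (a, b) with |z| > 1.96, or with two-sided Fisher p ≤ 0.05.

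**Where the test rejects.** With no control events, 6/20 gives z = 1.90 and 7/20 gives z = 2.10, so seven events are needed. With one control event, ten of 20 are needed. At true rates of 17% and 10%, P(no control event) = 0.9^10 = 0.349 and P(at least 7 of 20) = 0.041. The product is 0.0143, which is almost all of the power in the direction of harm.

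**Power at 20 vs 10**

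| True rates | Fisher | Rank-sum |
|---|---|---|
| 17% vs 10% | 0.8% | 2.3% (1.45% towards harm) |
| 17% vs 11% | 0.9% | 2.3% |
| 30% vs 10% | 9.8% | 15.7% |
| 50% vs 10% | 54% | 61% |
| 60% vs 10% | 74% | 81% |

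With 17 vs 8 patients, 17% vs 10% gives 0.4% (Fisher) and 1.7-2.2% (rank-sum, with and without continuity correction). A normal approximation gives 5.9% at 20 vs 10, but it is unreliable with one expected control event (10 × 0.10).

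**What intervals would show instead**
- No events in 20: the exact two-sided 95% upper limit is 1 − 0.025^(1/20) = 16.8%. For 0/17 it is 1 − 0.025^(1/17) = 19.5%.
- 3/20 vs 1/10: the difference is 0.15 − 0.10 = +5 points and Fisher p = 1.0. The Wilson limits are 5.2% to 36.0% and 1.8% to 40.4%. Newcombe's limits for the difference are:
  - lower: 0.05 − √[(0.150 − 0.052)² + (0.404 − 0.100)²] = −0.27
  - upper: 0.05 + √[(0.360 − 0.150)² + (0.100 − 0.018)²] = +0.28

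The p-value of 1.0 and the interval from −27 to +28 points describe the same data. Only the interval shows that a large excess has not been excluded.

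**The case against.** The best case for the plan has four parts.

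1. **No decision rule is written.** A reader might infer that the protocol will declare the drug safe if p exceeds 0.05. It does not say so. It sets no alpha and nowhere equates non-significance with safety. This stands: the documents show a risk of misreading, not a planned one.

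2. **Safety is already described, not only tested.** Percentages by severity are the planned measure, Section 10.0 adds mortality, and Section 8.11 adds laboratory monitoring. The GASE form also asks whether each complaint is related to medication. This stands too, so it would be wrong to call the test the whole safety assessment. What is missing is any measure of uncertainty around those percentages.

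3. **Diarrhea is one item among more than 30 on GASE.** The endpoint is aggregate percentages from weekly prompted reports over 14 weeks, and those rates may be higher than the cited ones. A reader might take 1-2% as the power of the safety analysis. It is not. The documents give no expected aggregate rates, so that power cannot be computed.

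4. **Low power for a 7-point excess is normal in a pilot, and the test is not blind.** Both are true. Rank-sum power is about 61% at 50% vs 10% and 81% at 60% vs 10%, so it would be too broad to say that almost any side-effect profile would pass. Section 8.1 also describes the diarrhea as mostly mild or moderate and short-lived. None of this supports the word determine in Section 10.0: a pilot of this size can estimate rates, and the point does not ask for a larger one.

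**Conclusion.** The point holds in a limited form. Sections 10.0 and 13.1 attach a conclusion about safety to a comparison that cannot support it at 25-30 patients, and they plan no interval that would show what the data leave open. For the one effect with rates in the protocol, the chance of a significant result is 0.8-2.3%. For a tripled rate (30% vs 10%) it is 10-16%, so the test would miss it about 84-90% of the time. The figures assume two-sided alpha 0.05, 20 vs 10 patients, no dropout and one yes/no outcome per patient. At 25 patients the result for 17% vs 10% is similar or lower.

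This is a fault of analysis and wording, not of sample size, and it is cheap to correct.

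**What to change.** - **Section 13.1:** make estimation the main safety analysis. Report the planned side-effect percentages for each arm with exact (Clopper-Pearson) 95% intervals, and the risk difference with a 95% interval such as Newcombe's. Count each patient once per category, because exact binomial limits do not apply to repeated weekly reports. The rank-sum test may stay as a secondary analysis, with its alpha stated.
- **Section 10.0:** replace determine with estimate. Add that safety will be described by the upper confidence limits and will not be inferred from a non-significant p-value.

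The cost is a change of wording in two sections, with no added patients, visits or data. The downside is a less favourable claim: even with no events in 20 patients, the report would have to say that a true rate of up to 16.8% is not excluded.
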